### 5.3 OPEN-LABEL EXTENSION (OLE) PERIOD

All patients who complete the core study (Screening and DPC period) on study medications (octreotide capsules or placebo), or patients who met the pre-defined withdrawal criteria and were followed per protocol until week 36 on prior SRL injections (as rescue medication), will be offered to enter the OLE period and receive octreotide capsules until the last patient enrolled completes one year or until product marketing or study termination. Beyond one year, the Sponsor will either extend the OLE period (via protocol amendment for an additional one year or until product marketing or study termination) or consider compassionate (if requested by the principal investigator under compassionate use protocol).

During the OLE period the initial octreotide capsules dose will be 60 mg for all patients. The dose can be escalated or de-escalated upon the investigator's discretion, based on either IGF-1 and/or safety and tolerability (See [Section 6.2](#)).

All patients will be contacted by phone after two weeks. The following assessments and procedures will be performed on the pre-scheduled telephone calls at Week 2:

- AEs recording
- Compliance assessment and drug administration instructions (including dose titrations)
- Address any potential questions the patient may have with the new treatment

Clinic visits will be scheduled to occur every 4 weeks ( $\pm 3$  days) for the initial 24 weeks, at weeks 36, 46 and 48 and every 12 weeks ( $\pm 10$  days) thereafter. An additional visit at OLE week 46 will be conducted to collect IGF-1 samples.

The following procedures will be done on OLE visits:

- Octreotide capsules administration at the site
- Safety laboratory tests: hematology, biochemistry, urinalysis, TSH, free T4, and lipid profile (total cholesterol, triglycerides, high-density lipoprotein, and low-density lipoprotein); HbA1c will be done every six months
- Serum pregnancy test every six months
- Weight
- Vital signs
- Acromegaly directed and treatment directed physical examination
- AEs and concomitant medications recording
- Dispense study medication (call IVRS/IWRS)
- Study medication accountability
- IGF-1 (OLE Months 3 and 6 followed by every six months, including OLE week 46 and 48)
- GH (OLE Month 6, Month 12, annually thereafter and last visit of OLE period)
- Abdominal gall bladder (every six months)

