AEs will be assessed at all study visits throughout the study from informed consent signing. AEs reported prior to dosing on Baseline Day will be captured and considered non-treatment emergent AEs. Treatment Emergent AEs (TEAEs) will be considered all AEs that occurred from Baseline (following study medication administration) to end of core study (i.e. end of DPC period). AEs reported after termination/completion of the core study, during the Follow-up period will be reported separately. AEs reported during the OLE period will be reported separately and together with the core study. The final safety analysis will be detailed in the Statistical Analysis Plan (SAP). The date and time of each AE occurrence will be recorded.

All AEs, whether observed by the Investigator or designee or volunteered by the patient, should be recorded individually on an AE eCRF page with the following information: the specific event or condition, whether the event was present pre-study (and if so, should be captured in the medical history eCRF page), the dates and times (using the 24 hour clock, where midnight is 00:00 and noon is 12:00) of occurrence, duration, severity, relationship to study medication, specific countermeasures, outcome, and whether considered non-serious or serious, drug-related or not. AEs will be recorded from the time a patient has signed the informed consent form (ICF) and throughout the study, including the Core study, Follow-up and OLE period. Severity of the AE will be assessed by the Investigator in accordance with the definitions below. An SAE must fulfill the requirements listed in the [Section 7.2](#).

Three definitions only should be used by the investigating physician to describe the severity of the AE ([Table 1](#)). Only one severity (the worst severity) definition should be used for each AE (e.g., "mild/moderate" is not acceptable).

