### **Common Gastrointestinal Adverse Events**

In the previous Phase 3 Study (CH-ACM-01), GI symptoms were among the most commonly reported AEs. These AEs were generally transient and declined with time (median duration was 13 days). Most were mild to moderate in intensity, and occurred during the first two months. There was no dose relationship and most resolved with treatment continuation.

In patients who develop abdominal symptoms (e.g., nausea, vomiting, abdominal pain or diarrhea), common GI illnesses should be excluded (e.g., gastroenteritis, cholestasis, etc.), and treated accordingly. If symptoms are mild to moderate in intensity and patient is able to tolerate oral medications, consideration should be given to treating the patient symptomatically with anti-emetics or anti-diarrheals to determine if patient's GI symptoms will resolve on therapy. Patients who have severe or persistent symptoms or who cannot tolerate food/fluids should be discontinued.

Of note, a phase 1 study showed no interaction between loperamide and oral octreotide capsules.

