## **1 Introduction**

This Statistical Analysis Plan (SAP) contains a more technical and detailed elaboration of the principal features of the analysis described in the protocol, and includes detailed procedures for executing the statistical analysis. This SAP should be used in conjunction with the protocol. If there are any discrepancies between the protocol and SAP, this SAP will prevail. Any deviations from this SAP that are implemented in the final analysis will be documented with sound clinical and statistical rationale in the Clinical Study Report (CSR). In the event of any changes to the primary endpoints or analyses, these changes will be documented through a protocol amendment, consistent with ICH E9.

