### 4.4 Open Label Extension Sets

For the OLE phase, several different analysis sets will be defined.

1. The open label extension (OLE) set will consist of all patients enrolled into the OLE phase of the study who receive at least one dose of open label study drug.
2. Octreotide capsule patients from the DPC period who enrolled into the OLE phase and received at least one dose of open label study drug (OLE-OCT)
3. Octreotide capsule patients from the DPC period, who were classified as treatment responders based on the primary endpoint, at the end of the DPC period, and who enrolled into the OLE phase and received at least one dose of open label study drug (OLE-OCT-RESP).

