## 6.9 Safety Analyses

All safety analyses for data collected during the DPC period will be presented using the safety set. All safety analyses for data collected during the OLE will be presented using the OLE set (summaries by treatment group will be based on the treatment group in the DPC period). Safety analyses for the DPC period will only use data collected during the DPC period, and will exclude any safety data that was collected after a subject had discontinued study drug. Safety analyses for the OLE will include data collected during the OLE. No formal hypothesis testing will be conducted. Data will be summarized using appropriate descriptive statistics. Missing data will be maintained as missing, unless indicated.

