### **6.9.1.2 OLE Phase**

Octreotide capsules can be up-titrated or down titrated during the OLE. All patients will start on 60 mg/day and can either down titrate to 40 mg/day or up titrate to 80 mg/day, based on clinical and biochemical response.

In the OLE, the duration of study drug exposure (in days) will be summarized by the treatment group and overall, using descriptive statistics. Duration of study drug exposure will be calculated as date of last dose in the OLE– date of first dose in the OLE + 1.

The number and proportion of patients at each dose level (40, 60 and 80 mg/day) at the end of the OLE, will also be presented by treatment group and overall.

Compliance to each dose level of octreotide capsules from first dose in the OLE through the last visit of the OLE will be calculated and summarized by treatment group and overall, and also by the final target dose level achieved within each treatment group during the OLE.

For the purpose of analysis, compliance to each dose level during the OLE will be calculated as  $100 \times (\text{total number of capsules actually taken} / \text{total number of capsules expected to be taken})$ . This calculation will be used for each dose level the patient received during the OLE. The numbers and percentages of patients <75% compliant, 75-100% compliant, and >100% compliant will be tabulated.

The number of actual capsules taken for each dose level will be the total number of capsules dispensed – total number of capsules returned during the time the patient was on that particular dose.

The number of expected capsules taken for the target dose level will be derived as follows:

Dose Level	Expected Number of Capsules Taken
40 mg	2 capsules × (first day of the phase – last day of the phase)
60 mg	3 capsules × (first day of the phase – last day of the phase)
80 mg	4 capsules × (first day of the phase – last day of the phase)
Overall	Sum of expected number of capsules taken over all of the dose levels assigned

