#### **6.9.2.2 OLE**

AEs will be considered treatment emergent for the purpose of reporting in the OLE if they meet any of the following criteria:

- AE onset date is after the end of treatment in the DPC period (i.e., date of onset greater than the end of treatment date in the DPC period)
- AE is ongoing, and the severity worsens during the OLE (i.e., date of severity worsening is greater than the end of treatment date in the DPC period)

All summaries will be presented by final dose group (i.e., 40, 60 or 80) and overall for the OLE set.

If the day of onset of an AE is missing, then if the month and year of an onset date are on or after the date of randomization, the following rules will be applied:

- If month/year of the onset date is on or after the month/year of the end of treatment date in the DPC period, the AE will be considered treatment emergent;
- If month/year of the onset date is equal to the month/year of the end of treatment date in the DPC period, and the end date is present, the end date will be used to determine when the AE started. If the end date is on or after the end of treatment date in the DPC period, the AE will be considered treatment emergent; otherwise, if the AE stopped before randomization, then it will not be considered treatment emergent;
- If month/year of the onset date is equal to the month/year of the end of treatment date in the DPC period, and the end date is a partial date, the AE will be considered treatment emergent;
- If, despite implementing the above conventions, the onset date of the AE cannot be placed before, on, or after the end of treatment date in the DPC period, then the event will be considered treatment emergent.

Summaries of TEAEs will be presented using the MedDRA level hierarchy (system organ class, high level group term, high level term, and preferred term) as follows:

Overall (i.e., regardless of intensity or relationship to treatment)

By intensity grade (mild, moderate, severe)

By relationship to study medication (potential relationship to study treatment or unlikely/no relationship to study treatment) according to the mapping scheme below:

Related: will include all AEs with a relationship rating of “related” or “possibly related”

Not related: will include all AEs with a relationship rating of “Not related”

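### The main OLE adverse-event tables pool patients on their first octreotide capsule with patients who have had up to 36 weeks of capsules, and no planned adverse-event table joins the two periods

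*SAP*

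**What the plan says.** - **Who is in the OLE tables.** SAP 4.4: "The open label extension (OLE) set will consist of all patients enrolled into the OLE phase of the study", given at least one open-label dose. Protocol 5.3 offers the extension to completers from either arm, and to patients who met the withdrawal criteria and were followed to week 36 on injections.
- **Layout.** SAP 6.9.2.2: "All summaries will be presented by final dose group (i.e., 40, 60 or 80) and overall for the OLE set". Protocol 8.4.8.1 carries the identical sentence.
- **Exceptions.** SAP 6.9.2.2 adds treatment group for serious TEAEs and for TEAEs leading to discontinuation. SAP 6.9 fixes what treatment group means in the OLE: "summaries by treatment group will be based on the treatment group in the DPC period".
- **Clocks.** An OLE TEAE is one that starts, or worsens, after the end-of-treatment date in the DPC period. SAP 6.9.1.2 counts OLE exposure as the last OLE dose date minus "date of first dose in the OLE + 1", by treatment group and overall.
- **Combined reporting.** Protocol 7.1: "AEs reported during the OLE period will be reported separately and together with the core study", with the detail left to the SAP. Protocol 8.4.8 and SAP 6.9 describe DPC analyses on DPC data and OLE analyses on OLE data. SAP 1: "If there are any discrepancies between the protocol and SAP, this SAP will prevail".
- **Timing of events.** Protocol 7.6, on gastrointestinal events in the earlier phase 3 study: "Most were mild to moderate in intensity, and occurred during the first two months".

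**The concern.** The OLE objective is long-term safety. At OLE entry the two former arms are at different points in their treatment. Former placebo patients are starting capsules. Most former octreotide patients are continuing and have already shown that they tolerate capsules. If start-up events dominate early, as the sponsor's own experience suggests, one pooled incidence describes neither group.

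The events most affected are mild to moderate gastrointestinal events. These fall in the overall, intensity and relationship tables, which are the ones not split by prior arm. For the former octreotide arm, the adverse-event and exposure record is also cut in two at OLE entry, and no planned table puts it back together.

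**Working it through.** The plan states no figure to reproduce, so the main check is of the text.

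**1. Which OLE tables separate the prior arms?**

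| OLE summary | By final dose | By DPC arm |
|---|---|---|
| TEAEs overall, by intensity, by relationship (SAP 6.9.2.2) | yes | no |
| Serious TEAEs; TEAEs leading to discontinuation (SAP 6.9.2.2) | yes | yes |
| OLE exposure (SAP 6.9.1.2) | number at each dose | yes |
| Laboratory, vital signs, ECG (SAP 6.9.3 to 6.9.5) | yes | yes |
| AESIs | none named for the OLE | none named for the OLE |

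The main TEAE tables are the exception among the OLE safety summaries.

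**2. Can final dose stand in for prior arm?** No. Everyone starts the OLE at 60 mg (SAP 6.9.1.2). The guidance in protocol 6.2 lists moderate to severe gastrointestinal symptoms, with controlled IGF-1 and acromegaly symptoms, as one ground for moving down. Final dose can therefore be a result of the event being tabulated, and prior exposure cannot be recovered from it.

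**3. Is combined reporting planned?** Protocol 7.1 says yes. Protocol 8.4.8 and 8.4.8.1 define separate periods with separate TEAE windows, and SAP 6.9, 6.9.2.1 and 6.9.2.2 repeat them. The SAP's safety section is not redacted and contains no combined table. The conflict lies inside the protocol, and the SAP follows one side of it.

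**4. The clocks.** Take a patient treated throughout, at OLE week 48:

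- former octreotide: 36 + 48 = 84 weeks since first capsule, reported as 36 weeks in the DPC summary and 48 in the OLE summary;
- former placebo: 48 weeks since first capsule, reported as 48.

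Taking 12 months as 52 weeks, the former octreotide patient reaches 12 months of capsules at OLE week 52 − 36 = 16, and the former placebo patient at OLE week 52. No planned table shows this. For the earlier phase 3 study, protocol 1.3 does report exposure over core plus extension and the number exposed for more than 12 months (82 of 155 patients, 53%).

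**5. Rescued patients.** The OLE TEAE window opens after the last blinded dose, not at the first OLE capsule. By that date rule, an event that starts on rescue injections before any OLE capsule would count as an OLE TEAE. SAP 6.9 says that OLE analyses include data collected during the OLE, but it does not say that this overrides the date rule.

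**6. Illustration of the pooling.** Let w be the former placebo share of the OLE set, p1 the incidence in first-exposed patients and p2 the incidence in continuing patients. The pooled incidence is w·p1 + (1 − w)·p2. The documents give none of these values. Assume w = 0.5, p1 = 40 to 60% and p2 = 10 to 20%:

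- lowest pooled value: (40 + 10)/2 = 25%; highest: (60 + 20)/2 = 40%;
- distance from either group = (p1 − p2)/2, from (40 − 20)/2 = 10 to (60 − 10)/2 = 25 points;
- if p1 = p2, the distance is 0.

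With p1 = 40% and p2 = 10%, moving w from 0.4 to 0.6 moves the pooled figure from 22% to 28%.

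**The case against.** Several stronger readings are tempting, and the documents do not support them.

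- **That the SAP dropped a protocol promise.** Protocol 8.4.8 plans separate periods too, so the SAP mirrors the protocol's own statistical section. The precedence clause does not clearly settle the matter either. It applies to discrepancies, and silence may not be one. SAP 6.9 also restricts DPC analyses to DPC data with the word only, but does not use that word for the OLE.
- **That all OLE safety data are pooled.** Serious TEAEs, discontinuations for TEAEs and exposure are shown by DPC arm.
- **That nothing is measured from first exposure.** For the former placebo arm, the first OLE dose is the first octreotide capsule. For the former octreotide arm, laboratory, vital-sign and ECG changes use the DPC baseline, which is the start of capsules. The gap concerns adverse events and exposure.
- **That one-year exposure cannot be known.** DPC and OLE exposure are derived for each patient and can be added. What is missing is a planned table.
- **That the first 36 weeks are lost.** They are in the DPC tables, against a randomized placebo group, which is the best place to read start-up events.
- **That every former octreotide patient has had 36 weeks of capsules.** Rescued patients had less, which is why the figure is up to 36 weeks.

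It can also be said that the OLE carries no hypothesis and that, with about 25 patients per arm before attrition, finer tables will be sparse. Both points are true. They limit the weight of the concern and argue for a modest remedy. They do not justify a pooled main table.

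**Conclusion.** The point holds as a reporting weakness. The main OLE TEAE tables mix first-exposed and continuing patients, final dose does not separate them, and the combined reporting in protocol 7.1 has no counterpart in protocol 8.4.8 or SAP 6.9. For the former octreotide arm, no planned adverse-event or exposure table runs from first capsule across both periods. The OLE TEAE window may also take in events on rescue injections.

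The size of the distortion cannot be known from the documents. The 10 to 25 points rest on assumed incidences and an equal mix, and the distortion vanishes if the two groups have the same incidence. No confirmatory test is affected. The change is still worth making, because it bears directly on the OLE's stated objective and needs only data that are already collected.

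**What to change.** 1. In SAP 6.9.2.2 and protocol 8.4.8.1, show all OLE TEAE tables, and any OLE AESI tables, by DPC arm (prior octreotide, prior placebo) as well as by final dose and overall.
2. In SAP 6.9.1 and 6.9.2, add one combined table of all octreotide-capsule exposure (DPC octreotide plus OLE), timed from each patient's first octreotide capsule and excluding time off capsules on rescue. It should give total exposure, the number treated for at least 12 months, and TEAE incidence with an exposure-adjusted rate. Bands of time since first capsule are optional.
3. Reconcile protocol 7.1 with protocol 8.4.8 and SAP 6.9. State there how events between the last blinded dose and the first OLE capsule are classified.

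The cost is some SAP and protocol wording and a re-tabulation of existing data. No visit, treatment or hypothesis test changes. The downside is a few more descriptive tables with small cells, at most about 25 patients per prior arm.

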### **6.9.3 Laboratory Parameters**

Descriptive summary statistics for chemistry and hematology data at each post randomization time point (both absolute and change) will be presented by final dose group and treatment group (i.e., octreotide 40, 60, 80, overall and placebo). Summaries will be provided for the DPC period and for the OLE period. In calculating the change from baseline for both the DPC and for the OLE, the baseline for the DPC period will be used.

Shift tables, summarizing individual subject changes from baseline to end of treatment will be presented for each laboratory parameter, by treatment group, using the normal ranges from the central laboratory. An additional shift analysis will be presented for glucose using the levels within the common terminology criteria for adverse events (CTCAE) version 4.03. Summaries will be provided for both the DPC period and OLE period. For both the DPC period and the OLE period summaries, baseline will be the baseline defined for the start of the DPC period.

Subjects with clinically significant abnormalities (based on investigator’s assessment) will be identified in listings.

All tabular summaries will exclude any data that was collected after a subject had discontinued study drug. Data collected after a subject had discontinued study drug will be included in listings.

